### 10.2.2. Treatment States

Assessments and events will be classified according to time of occurrence relative to the start and/or stop date of the study treatment.

#### 10.2.2.1. Treatment States for AE Data

Treatment State	Definition
Pre-Treatment	AE Start Date $<$ Study Treatment Start Date
On-Treatment	If AE onset date is on or after treatment start date & on or before the treatment stop date Study Treatment Start Date $\leq$ AE Start Date $\leq$ Study Treatment Stop Date [+ 1]
Post-Treatment	If AE onset date is after the treatment stop date AE Start Date $>$ Study Treatment Stop Date
Onset Time	If Treatment Start Date $>$ AE Onset Date = AE Onset Date - Treatment Start Date
Since First Dose (Days)	If Treatment Start Date $\leq$ AE Onset Date = AE Onset Date - Treatment Start Date + 1 Missing otherwise
Duration (Days)	AE Resolution Date – AE Onset Date + 1
Drug-related	If relationship is marked 'YES' on eCRF OR value is missing

#### NOTES:

- If the study treatment stop date is missing then the AE will be considered to be On-Treatment.

## 10.3. Appendix 3: Data Display Standards & Handling Conventions

### 10.3.1. Study Treatment & Sub-group Display Descriptors

Treatment Group Descriptions			
RandAll NG		Data Displays for Reporting	
Code	Description	Description	Order [1]
A	GSK2269557 500 mcg	GSK2269557 500 mcg	1
B	GSK2269557 750 mcg	GSK2269557 750 mcg	2

**NOTES:**

1. Order in which treatments are to be presented in Tables, Figures and Listings.

### 10.3.2. Baseline Definition & Derivations

#### 10.3.2.1. Baseline Definitions

For all endpoints the baseline value will be the latest pre-dose assessment.

#### 10.3.2.2. Derivations and Handling of Missing Baseline Data

Definition	Reporting Details
Change from Baseline	= Post-Dose Visit Value – Baseline

**NOTES :**

- Unless otherwise specified, the baseline definitions specified in Section 10.3.2.1 Baseline Definitions will be used for derivations for endpoints / parameters and indicated on summaries and listings.
- Unless otherwise stated, if baseline data is missing no derivation will be performed and will be set to missing.
- The baseline definition will be footnoted on all change from baseline displays.

### 10.3.3. Reporting Process & Standards

Reporting Process	
Software	

 
• The currently supported versions of SAS software will be used.
 
	
Reporting Area	
HARP Server	: uk1salx00175
HARP Area	: \arprod\gsk2269557\mid207674\final_01
QC Spreadsheet	: \ARWORK\gsk2269557\mid207674\Final_01\Documents
Analysis Datasets	

 
• Analysis datasets will be created according to CDISC standards
 
	
Generation of RTF Files	

 
• RTF files for tables will be generated.
 
	

Reporting Standards	
General	

 
The current GSK Integrated Data Standards Library (IDSL) will be applied for reporting, unless otherwise stated: 
 
4.03 to 4.23: General Principles
 
5.01 to 5.08: Principles Related to Data Listings
 
6.01 to 6.11: Principles Related to Summary Tables
 
7.01 to 7.13: Principles Related to Graphics
 
 
 
	
Formats	

 
GSK IDSL Statistical Principles (5.03 & 6.06.3) for decimal places (DP's) will be adopted for reporting of data based on the raw data collected
 
Numeric data will be reported at the precision collected on the eCRF.
 
The reported precision from non eCRF sources will follow the IDSL statistical principles but may be adjusted to a clinically interpretable number of DP's.
 
	
Planned and Actual Time	

 
Reporting for tables and figures: 
 
Planned time relative to dosing will be used in figures and summaries and calculation of any derived parameters, unless otherwise stated.
 
The impact of any major deviation from the planned assessment times and/or scheduled visit days on the analyses and interpretation of the results will be assessed as appropriate.
 
 
 
Reporting for Data Listings: 
 
Planned and actual time relative to study drug dosing will be shown in listings.
 
Unscheduled or unplanned readings will be presented within the subject's listings.
 
Visits outside the protocol defined time-windows (i.e. recorded as protocol deviations) will be included in listings but omitted from figures and summaries.
 
 
 
	
Unscheduled Visits	

 
Unscheduled visits will not be included in summary tables.
 
Unscheduled visits will not be included in figures.
 
All unscheduled visits will be included in listings.
 
	
Descriptive Summary Statistics	
Continuous Data	Refer to IDSL Statistical Principle 6.06.1
Categorical Data	N, n, frequency, %
Reporting of Pharmacokinetic Concentration Data	
Descriptive Summary Statistics	Refer to IDSL Statistical Principle 6.06.1 Assign zero to NQ values (Refer to GUI_51487 for further details)
Reporting of Pharmacokinetic Parameters	
Descriptive Summary	N, n, geometric mean, 95% CI of geometric mean, standard deviation

Reporting Standards	
Statistics. (Log Transformed)	(SD) of logged data and between geometric coefficient of variation (CVb (%)) will be reported. $CVb (\%) = \sqrt{(\exp(SD^2) - 1)} * 100$ [NOTE: SD = SD of log transformed data]
Parameters Not Being Log Transformed	tmax, first point, last point and number of points used in the determination of Lambda_z.
Parameters Not Being Summarised	Additionally include tmax, first point, last point and number of points used in the determination of Lambda_z.
Listings	Include the first point, last point and number of points used in the determination of Lambda_z.
Graphical Displays	

 
Refer to IDSL Statistical Principles 7.01 to 7.13.
 
	

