9.3.5. Clinical Safety Laboratory Assessments

- Refer to [Appendix 6](#) for the list of clinical laboratory tests to be performed and to the SoA for the timing and frequency.
- The investigator must review the laboratory report, document this review, and record any clinically relevant changes occurring during the study in the AE section of the CRF. The laboratory reports must be filed with the source documents. Clinically significant abnormal laboratory findings are those which are not associated with the underlying disease, unless judged by the investigator to be more severe than expected for the participant's condition.
- All laboratory tests with values considered clinically significantly abnormal during participation in the study should be repeated until the values return to normal or baseline or are no longer considered significantly abnormal by the investigator or medical monitor.
- If such values do not return to normal/baseline within a period of time judged reasonable by the investigator, the etiology should be identified and the sponsor notified.
- All protocol-required laboratory assessments, as defined in [Appendix 6](#), must be conducted in accordance with the laboratory manual and the SoA.
- If laboratory values from non-protocol specified laboratory assessments performed at the institution's local laboratory require a change in participant management or are considered clinically significant by the investigator (eg, SAE or AE or dose modification), then the results must be recorded in the CRF.

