## 10.4. Appendix 4: Derived and Transformed Data

### 10.4.1. General

Multiple Measurements at One Time Point

 
Mean of the measurements will be calculated and used in any derivation of summary statistics but if listed, all data will be presented.
 
If there are two values within a time window the value closest to the target day for that window will be used. If values are the same distance from the target then the mean will be taken.
 
Subjects having both High and Low values for Normal Ranges at any post-baseline visits for safety parameters will be counted in both the High and Low categories of “Any visit post-baseline” row of related summary tables. This will also be applicable to relevant Potential Clinical Importance summary tables.
 

FEV1 and FVC measurements

 
FEV1 and FVC measurements are to be taken in triplicate, the maximum of the values entered at one time point will be used for the summaries and listings of FEV1 and FVC
 

Study Day

 
Calculated as the number of days from randomisation date : 
 
Ref Date = Missing → Study Day = Missing
 
Ref Date < Randomisation Date → Study Day = Ref Date – Randomisation Date
 
Ref Date ≥ Randomisation Date → Study Day = Ref Date – (Randomisation Date) + 1
 
 
 

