#### 10.8.4. Safety Tables

Safety Tables					
No.	Population	IDSL / TST ID / Example Shell	Title	Programming Notes	Deliverable [Priority]
Adverse Events					
2.1	Safety	CP_AE1p	Summary of All Adverse Events		SAC [1]
2.2	Safety	CP_AE1p	Summary of All Drug-Related Adverse Events	Include total column.	SAC [1]
2.3	Safety	CP_AE1p	Summary of Serious Adverse Events		SAC [1]
2.4	Safety	AE15	Summary of Common (>=5%) Non-serious Adverse Events by System Organ Class and Preferred Term (Number of Subjects and Occurrences)		SAC [1]
2.5	Safety	CP_AE1p	Summary of Adverse Events Leading to Permanent Discontinuation of Study Drug or Withdrawal from Study		SAC [1]
Labs					
2.6	Safety	LB1	Summary of Chemistry Changes from Baseline		SAC [1]
2.7	Safety	LB17	Summary of Emergent Chemistry Results by Potential Clinical Importance (PCI) Criteria		SAC [1]
2.8	Safety	LB1	Summary of Haematology Changes from Baseline		SAC [1]
2.9	Safety	LB17	Summary of Emergent Haematology Results by Potential Clinical Importance (PCI) Criteria		SAC [1]

Safety Tables					
No.	Population	IDSL / TST ID / Example Shell	Title	Programming Notes	Deliverable [Priority]
2.10	Safety	UR3b (LB1)	Summary of Urinalysis Results by Planned Timepoint	Use shell UR3b for: pH, glucose, protein, blood, ketones, bilirubin, urobilinogen, nitrite, leukocyte esterase as these are collected by dipstick  Use shell LB1 for: Specific gravity	SAC [1]
ECGs					
2.11	Safety	EG1	Summary of ECG Findings		SAC [1]
2.12	Safety	EG2	Summary of ECG Values		SAC [1]
2.13	Safety	EG2	Summary of Change from Baseline in ECG Values		SAC [1]
Vital Signs					
2.14	Safety	VS1	Summary of Change from Baseline in Vital Signs		SAC [1]
2.15	Safety	VS7	Summary of Emergent Vital Signs Results by Potential Clinical Importance (PCI) Criteria		SAC [1]
Spirometry					
2.16	Safety		Summary of Spirometry (FVC and FEV1)	See example: uk1salx00175/gsk2269557/mid205759/final/Table 2.35	SAC [1]
2.17	Safety		Summary of Change from Baseline in Spirometry (FVC and FEV1)	See example: uk1salx00175/gsk2269557/mid205759/final/Table 2.38	SAC [1]

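### The any-visit rows of the PCI safety tables omit unscheduled and out-of-window values, so for chemistry and haematology they cover Day 2 only

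*SAP*

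**What the plan says.** SAP 10.3.3 (Reporting Process & Standards) has two exclusion rules. On unscheduled visits: "Unscheduled visits will not be included in summary tables". They are barred from figures too, and sent elsewhere: "All unscheduled visits will be included in listings". On out-of-window visits, meaning those recorded as protocol deviations, the values "will be included in listings but omitted from figures and summaries". Neither rule makes an exception for safety tables.

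SAP 10.4.1 (General) says how to count a participant who has both a High and a Low value after baseline: in both categories of the Any visit post-baseline row. It then adds: "This will also be applicable to relevant Potential Clinical Importance summary tables". It does not say whether unscheduled visits belong in that row.

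By title, the PCI summary tables in SAP 10.8.4 are Table 2.7 ("Summary of Emergent Chemistry Results by Potential Clinical Importance (PCI) Criteria"), Table 2.9 for haematology and Table 2.15 for vital signs.

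Protocol Section 2 schedules laboratory tests at Screening, Day -1 and Day 2. Protocol 9.3.5 says that results judged clinically significantly abnormal "should be repeated until the values return to normal or baseline" or are no longer judged significant. Protocol Section 9 allows repeat or unscheduled samples for safety reasons or for technical problems with a sample.

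**The concern.** A row labelled as covering any post-baseline visit tells the reader that it holds each participant's worst post-dose result. Under 10.3.3 it holds only planned, in-window results. Where there is one planned post-dose draw, the label and the content differ: any visit means Day 2.

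Safety and tolerability are the secondary objective, and the PCI tables are the displays that apply fixed thresholds regardless of clinical judgement. With six participants per arm, one uncounted participant changes the row visibly. A reader who relies on the table would see no participant above a threshold when the listing shows one.

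**Working it through.** The plan gives no figure to reproduce here. The check sets the rules beside the schedule and then scales the result.

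**1. What the row can contain.** Planned post-dose readings in Protocol Section 2:

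- Chemistry and haematology: Day 2 only, one draw.
- Vital signs: 1 h and 6 h on Day 1, and Day 2, so three readings.

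After both exclusions in SAP 10.3.3, the any-visit row for Tables 2.7 and 2.9 reduces to the Day 2 value. For Table 2.15 it still spans three readings, but unscheduled visits remain outside it.

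**2. Sign that the two sections were not read together.** The High-and-Low convention in SAP 10.4.1 needs at least two post-baseline values of the same parameter. For chemistry and haematology there is one planned draw, and 10.4.1 reduces two values in one window to one (the closest to target, or the mean). With unscheduled visits excluded, the convention can never operate for these tests. It can operate for vital signs.

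**3. Which values drop out.**

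- *First crossing at an unscheduled check.* A participant is below every threshold on Day 2, is sampled again later for a safety reason, and then crosses one. The value is excluded.
- *Combined criterion met only on a repeat.* SAP 10.6.1 flags total bilirubin of 1.5xULN together with ALT of at least 2xULN. Suppose Day 2 shows ALT of at least 3xULN with normal bilirubin. Protocol Appendix 4 calls for repeat liver chemistries within 24 to 72 hours. If ALT is still at least 2xULN on the repeat and bilirubin has now reached 1.5xULN, the combined criterion is met for the first time. The Day 2 ALT is counted in Table 2.7; the combined criterion is not.
- *Out-of-window Day 2 visit.* The participant's only planned post-dose laboratory result leaves the summaries.

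**4. What does not drop out.** Under Protocol 9.3.5 the abnormal value comes first and the repeat follows. The first value is normally the scheduled Day 2 result, which stays in the table. If it already crosses a threshold, a worse repeat does not alter a once-per-participant count for that threshold.

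**5. Size, for illustration.** Planned numbers are 6 per arm and 12 in total (Protocol 10.1). Suppose one participant meets a criterion only through an excluded value. Exact (Clopper-Pearson) 95% intervals:

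| | Shown in table | All post-dose values counted |
|---|---|---|
| One arm | 0/6 = 0% (0 to 45.9%) | 1/6 = 16.7% (0.4 to 64.1%) |
| Both arms | 0/12 = 0% (0 to 26.5%) | 1/12 = 8.3% (0.2 to 38.5%) |

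For example, the upper limit for 0/6 is 1 - 0.025^(1/6) = 0.459, and the lower limit for 1/6 is 1 - 0.975^(1/6) = 0.004. The intervals overlap widely, so the issue is the accuracy of a count and not a change in inference.

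**The case against.** The strongest reply is that nothing is lost. SAP 10.3.3 says "Unscheduled or unplanned readings will be presented within the subject's listings", and Listings 17 to 20, 24 and 25 show PCI values for chemistry, haematology and vital signs. With 12 participants each can be read individually. Abnormal results judged clinically significant are also adverse events (Protocol Appendix 5) and reach Tables 2.1 to 2.5, and the participant in the combined-criterion example would already be reported as a liver event. Keeping tables to planned visits is a reasonable convention that avoids unequal ascertainment, and no test depends on these counts.

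Much of this stands, and it limits the point to the counts in the tables. It does not make a count labelled as any visit correct. Adverse event status depends on the investigator's judgement, whereas PCI flags use fixed thresholds. The mandatory SAE rule for bilirubin starts at 2xULN with ALT of at least 3xULN, above the combined PCI criterion.

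Two further replies also stand. The rule speaks of visits, so an extra reading at a scheduled visit may fall under 10.4.1 instead. The table shells are not in the SAP, so whether each PCI table carries the row is inferred from 10.4.1.

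A reader might infer that the tables lose the abnormal values that prompt retesting, and so lean systematically towards no signal. The documents do not support that. The prompting value is normally the scheduled one and is kept, unscheduled samples may also be taken for technical reasons, and no frequency is given. A reader might also argue from the half-life of about 46 hours that late changes are being missed. That concerns having a single scheduled draw, which this counting rule neither causes nor could cure.

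**Conclusion.** The point holds as a modest table-count problem. As written, SAP 10.3.3 and 10.4.1 together make the any-visit row for chemistry and haematology a Day 2 row, and three kinds of post-dose value cannot enter it: a first crossing at an unscheduled check, a combined criterion first met on a repeat, and a Day 2 result from an out-of-window visit. For vital signs the row does not collapse to one reading, so the effect there is smaller.

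At most one participant per such event is uncounted, for example 0/6 shown instead of 1/6. How often this would happen is unknown. The conclusion assumes that the exclusions apply to the any-visit row, since no exception is written, and that the PCI shells contain it. The primary pharmacokinetic results are not affected.

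**What to change.** Add one sentence to SAP 10.3.3, with a cross-reference in 10.4.1, along these lines: *Unscheduled and out-of-window post-dose values are left out of by-timepoint summary statistics and figures, but count in the Any visit post-baseline rows of Tables 2.7 and 2.9 and, where the row exists, Table 2.15; each participant counts once per criterion.* State in the same place how an extra reading at a scheduled visit is treated.

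The cost is the sentence and a programming flag; no new data are needed. The downside is that participants who are checked more often have more chances to be flagged. Counting each participant once per criterion limits this, and a footnote giving the number flagged only through unscheduled or out-of-window values would make it visible.

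If the sponsor prefers planned visits throughout, the row should be relabelled as any scheduled post-baseline visit. That makes the label accurate but is less informative.

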## 10.4. Appendix 4: Derived and Transformed Data

### 10.4.1. General

Multiple Measurements at One Time Point

 
Mean of the measurements will be calculated and used in any derivation of summary statistics but if listed, all data will be presented.
 
If there are two values within a time window the value closest to the target day for that window will be used. If values are the same distance from the target then the mean will be taken.
 
Subjects having both High and Low values for Normal Ranges at any post-baseline visits for safety parameters will be counted in both the High and Low categories of “Any visit post-baseline” row of related summary tables. This will also be applicable to relevant Potential Clinical Importance summary tables.
 

FEV1 and FVC measurements

 
FEV1 and FVC measurements are to be taken in triplicate, the maximum of the values entered at one time point will be used for the summaries and listings of FEV1 and FVC
 

Study Day

 
Calculated as the number of days from randomisation date : 
 
Ref Date = Missing → Study Day = Missing
 
Ref Date < Randomisation Date → Study Day = Ref Date – Randomisation Date
 
Ref Date ≥ Randomisation Date → Study Day = Ref Date – (Randomisation Date) + 1
 
 
 

### 10.4.2. Study Population

Demographics
Age

 
GSK standard algorithms will be used for calculating age where birth date is imputed as: 
 
Any subject with a missing day will have this imputed as day ‘15’.
 
Any subject with a missing date and month will have this imputed as ‘30th June’.
 
 
 
Birth date will be presented in listings as ‘YYYY’.
 

Body Mass Index (BMI)

 
Calculated as <math>\text{Weight (kg)} / [\text{Height (m)}]^2</math>
 

Extent of Exposure

 
Number of days of exposure to study drug will be calculated based on the formula:  Duration of Exposure in Days = Treatment Stop Date – (Treatment Start Date) + 1 
 
Subjects who were randomized but did not report a treatment start date will be categorised as having zero days of exposure.
 

### 10.4.3. Safety

ECG Parameters
RR Interval

 
IF RR interval (msec) is not provided directly, then RR can be derived as :           
 
[1] If QTcB is machine read & QTcF is not provided, then :
 
 <math display="block">RR = \left[ \left( \frac{QT}{QTcB} \right)^2 \right] * 1000</math> 
 
[2] If QTcF is machine read and QTcB is not provided, then:
 
 <math display="block">RR = \left[ \left( \frac{QT}{QTcF} \right)^3 \right] * 1000</math> 
 

 
If ECGs are manually read, the RR value preceding the measurement QT interval should be collected values THEN do not derive.
 

Corrected QT Intervals

 
When not entered directly in the eCRF, corrected QT intervals using Bazett's (QTcB) and Fridericia's (QTcF) formulas will be calculated, in msec, depending on the availability of other measurements.
 
IF RR interval (msec) is provided then missing QTcB and/or QTcF will be derived as :
 
 $QTcB = \frac{QT}{\sqrt{\frac{RR}{1000}}}$ $QTcF = \frac{QT}{\sqrt[3]{\frac{RR}{1000}}}$

Adverse Events

 
MedDRA version 20.0 will be used for coding of AE's.
 

## 10.5. Appendix 5: Premature Withdrawals & Handling of Missing Data

### 10.5.1. Premature Withdrawals

Element	Reporting Detail
General	
 
Subject study completion is defined as subjects who receive study treatment and complete all post dose assessments, including the Follow Up Phone Call.
 
Withdrawn subjects maybe replaced in the study.
 
All available data from subjects who were withdrawn from the study will be listed and all available planned data will be included in summary tables and figures, unless otherwise specified.
 

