5.4. Scientific Rationale for Study Design

This is the first study that GSK2269557 will be administered via the ELLIPTA DPI formulated in a blend containing 0.4% MgSt. Magnesium stearate has been reduced in this final formulation from that studied in previous trials and has resulted in a change in the respirable mass of the drug product. It is anticipated that this will impact the PK profile in man and resulting in an increase in systemic exposure. Cmax may increase, by an average of approximately 50%-70% compared to the previously studied MgSt containing formulation. The final sampling timepoint (120 hours post-dose) has been

selected to confirm the terminal half-life based on preliminary data from study 205759 in healthy Japanese participants which has shown a half-life of approximately 46 hours.

This study will inform on the exposure of GSK2269557 administered via the ELLIPTA DPI formulated in the new blend containing 0.4% MgSt. Previous studies conducted across healthy participants and patients have shown no major differences in exposure.

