8.2. Withdrawal from the Study

- A participant may withdraw from the study at any time at his/her own request, or may be withdrawn at any time at the discretion of the investigator for safety, behavioral, compliance or administrative reasons.
- If the participant withdraws consent for disclosure of future information, the sponsor may retain and continue to use any data collected before such a withdrawal of consent.
- If a participant withdraws from the study, he/she may request destruction of any samples taken and not tested, and the investigator must document this in the site study records.
- Participants who are withdrawn will receive a follow-up telephone call at 10 – 12 days post dose. Refer to the SoA for data to be collected at the follow-up telephone call.

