## 4. ANALYSIS POPULATIONS

Population	Definition / Criteria	Endpoint(s) Evaluated
All Participants Enrolled (APE) Population	
 
All participants for whom a record exists on the study database; includes both screen participants and participants who are not screened but sign the informed consent form
 
	
 
Study Population
 

Safety	
 
All randomised participants who receive at least one dose of study treatment. Participants will be analysed according to the treatment they actually received.
 
	
 
Study Population
 
Safety
 

Population	Definition / Criteria	Endpoint(s) Evaluated
Pharmacokinetic	
 
• All randomised participants in the Safety population and for whom a pharmacokinetic sample was obtained and analysed.
 
	
 
• PK
 

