#### 7.1.3. Pharmacokinetic Parameters

##### 7.1.3.1. Deriving Pharmacokinetic Parameters

- Refer to [Appendix 4](#): Data Display Standards & Handling Conventions (Section [10.3.3](#) Reporting Process & Standards).
- The pharmacokinetic parameters will be calculated by standard non-compartmental analysis according to current working practices and using Win Nonlin Pro.
- All calculations of non-compartmental parameters will be based on actual sampling times recorded during the study.
- Pharmacokinetic parameters described in [Table 4](#) will be determined from plasma GSK2269557 concentration-time data, as data permits.

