**Table 4** **Derived Pharmacokinetic Parameters**

Parameter	Parameter Description
AUC(0-t)	Area under the concentration-time curve from time zero to the time of the last quantifiable concentration (C(t)) will be calculated using the linear trapezoidal rule for each incremental trapezoid and the log trapezoidal rule for each decremental trapezoid.
AUC(0-24)	
Area under the concentration-time curve will be calculated to fixed nominal time 24 hours after administration (AUC(0-24)), using the combination of linear and logarithmic trapezoidal methods (i.e., Linear Up/Log Down calculation method in Phoenix WinNonlin Professional).
 
If a sampling time deviation occurred at nominal time 24 hours after administration (and 24 < t), AUC(0-24) will be calculated using the concentration at time 24 hours after administration post-dose estimated by the method of interpolation.
 
If nominal time 24 hours after administration > t (or if the concentration at time 24 hours after administration was below then limit of quantification), then the concentration (y) at time 24 hours after administration is estimated using lambda_z and last observed Ct according to the formula:
 $y = Ct(\text{obser}) \times e^{-\lambda z(24-t)}$ 
Then the following equation will be used to calculate (AUC(0-24)) where t is the time of last quantifiable plasma concentration.
 $\text{AUC}(0-24) = \text{AUC}(0-t) + \text{AUC}(t-24)$ 
If lambda_z is not estimable, a partial AUC is not calculated (when 24 > t).

AUC(0- $\text{inf}^\infty$ )	
Area under the concentration-time curve from zero time (pre-dose) extrapolated to infinite time (AUC(0-inf)) will be calculated as follows:
 $\text{AUC}(0-\text{inf}) = \text{AUC}(0-t) + Ct / \lambda z.$
Cmax	Maximum observed concentration, determined directly from the concentration-time data.
tmax	Time to reach Cmax, determined directly from the concentration-time data.
Ctrough	Trough observed concentration, will be obtained directly from the concentration-time data.
t 1/2	
Apparent terminal half-life will be calculated as:
 $t_{1/2} = \ln 2 / \lambda z$ 
(NOTE: <math>\lambda z</math> is the terminal phase rate constant).

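### AUC(0-t) profiles cut short by withdrawal or a missed visit are averaged with 0-120 h profiles, because the SAP sets no common horizon and no exclusion

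*SAP*

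**What the plan says.** Five provisions act together.

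- **Withdrawn participants.** SAP 10.5.1 lists all their data and adds that "all available planned data will be included in summary tables and figures, unless otherwise specified". The PK sections (7.1, the PK rows of 10.3.3, Tables 3.3 and 3.4 in 10.8.5) make no exception for them.
- **PK population.** SAP section 4 requires only membership of the Safety population and that the participant be one "for whom a pharmacokinetic sample was obtained and analysed". No minimum profile is set.
- **AUC(0-t).** SAP Table 4 defines it as "Area under the concentration-time curve from time zero to the time of the last quantifiable concentration". The end point is specific to each participant, and the definition does not separate a concentration below the assay limit from sampling that stopped.
- **Lambda_z.** SAP 7.1.3.1 says that parameters "will be determined from plasma GSK2269557 concentration-time data, as data permits" and are calculated "according to current working practices". No minimum number of points, fit or time span is given. SAP 10.3.3 lists the points used for lambda_z but does not make them a criterion.
- **Sampling.** The protocol's schedule of activities takes late samples at 24, 48 and 120 h. Protocol 5.4 says that the last was "selected to confirm the terminal half-life based on preliminary data from study 205759 in healthy Japanese participants", about 46 h. After withdrawal, Protocol 8.2 provides a call only: "Participants who are withdrawn will receive a follow-up telephone call at 10 – 12 days post dose".

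Protocol 5.2 aims for six participants per arm with the 120 h sample and allows, but does not require, replacement. Neither document takes a replaced participant out of the PK summaries.

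**The concern.** AUC(0-t) is one of the primary PK parameters. Participants are discharged after the 24 h assessments, so someone who leaves after that loses the 48 h and 120 h samples, and someone who misses only Day 6 loses the 120 h sample. With a half-life near 46 h, a large part of the 0-120 h area lies beyond either point. The plan puts these shorter areas into the same geometric mean, confidence interval and CVb as the full ones, under one label. The mean falls and the apparent between-participant variability rises, for a reason unrelated to the drug or the formulation. With six per arm, one profile is enough to show. If no rule is set in advance, a decision after unblinding to drop one of six profiles would look data-driven.

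**Working it through.** **1. The protocol's own precision figures.** Protocol 10.1 gives log-scale SDs of 0.346 (Cmax) and 0.382 (AUC(0-24)) with n = 6. The half-width of the 90% CI is t(0.95; 5) × SD / √6:

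- Cmax: 2.015 × 0.346 / 2.449 = 0.285
- AUC(0-24): 2.015 × 0.382 / 2.449 = 0.314

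Both match the protocol, so its precision statement is per arm.

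**2. Illustrative profile (assumption).** C(t) = A·exp(−αt) + B·exp(−βt), with:

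- β = ln 2 / 46 (half-life from Protocol 5.4)
- A + B = 2.6 ng/mL and AUC(0-24) = 12.4 ng·h/mL (500 µg figures in the footnotes to Table 1, Protocol 5.5)
- α = ln 2 / h, with h = 0.5, 1, 2 or 3 h. The documents give no early half-life, so this is a range.
- all concentrations quantifiable to 120 h.

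AUC(0-T) = A(1 − e^(−αT))/α + B(1 − e^(−βT))/β.

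| Early half-life h | AUC(0-24) | AUC(0-48) | AUC(0-120) | ratio 24/120 | ratio 48/120 |
|---|---|---|---|---|---|
| 0.5 h | 12.4 | 20.0 | 31.6 | 0.393 | 0.634 |
| 1 h | 12.4 | 18.9 | 28.8 | 0.431 | 0.657 |
| 2 h | 12.4 | 16.4 | 22.4 | 0.553 | 0.730 |
| 3 h | 12.4 | 13.5 | 15.1 | 0.821 | 0.894 |

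**3. Effect on the arm's geometric mean.** One shortened profile with ratio r among n multiplies the geometric mean by r^(1/n).

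- Ends at 24 h, n = 6: 0.393^(1/6) = 0.856 to 0.821^(1/6) = 0.968, a fall of 3% to 14%.
- Ends at 24 h, replaced but kept (n = 7): 0.393^(1/7) = 0.875 to 0.821^(1/7) = 0.972, a fall of 3% to 13%.
- Ends at 48 h, n = 6: 0.634^(1/6) = 0.927 to 0.894^(1/6) = 0.981, a fall of 2% to 7%.

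**4. Effect on spread.** The expected log-scale variance becomes SD² + (ln r)²/n. Assume that the AUC(0-24) SD of 0.382 also applies to AUC(0-t). For one 24 h profile among six:

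- r = 0.393: √(0.382² + 0.934²/6) = 0.540, and the 90% half-width rises from 0.314 to 0.444.
- r = 0.821: SD 0.390, half-width 0.321.

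**5. Half-life and AUC(0-∞), if lambda_z were fitted to the last three points.**

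| Early half-life h | t½ from 6, 12, 24 h | AUC(0-∞) / true | t½ from 12, 24, 48 h | AUC(0-∞) / true |
|---|---|---|---|---|
| 0.5 h | 45.9 h | 1.00 | 46.0 h | 1.00 |
| 1 h | 37.1 h | 0.88 | 45.9 h | 1.00 |
| 2 h | 13.3 h | 0.63 | 37.5 h | 0.93 |
| 3 h | 5.3 h | 0.81 | 15.1 h | 0.90 |

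With the 24, 48 and 120 h points the fit returns 42 to 46 h. A profile ending at 24 h can therefore mislead badly or not at all. One ending at 48 h recovers the half-life unless the early phase is slow.

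**The case against.** **The carve-out and the wording of 10.5.1.** The clause carries an exception, and planned data can be read as scheduled assessments, in contrast to the unscheduled visits that SAP 10.3.3 keeps out of tables. SAP 10.5.2 also foresees exclusions, with reasons documented in the study report. This stands against any reading that withdrawn participants must enter every summary. It does not help AUC(0-t): no PK section uses the exception, and the samples at issue are scheduled ones.

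**Half-life and AUC(0-∞).** A reader might infer that the plan will report an early-phase half-life and that t½ and AUC(0-∞) are biased downwards. The documents do not support that. These parameters are derived only as data permit, under practices not set out in the SAP, so a poor fit may go unreported. The bias is also absent in the 0.5 h case. The lambda_z points are listed and individual profiles plotted (Figure 3.1), so a short fit would be visible. What stands is narrower: the acceptance rule is not stated.

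**Size.** The worst case of 14% is small beside the sampling error already accepted. With SD 0.382 and n = 6 the 95% CI factor is exp(2.571 × 0.382 / 2.449) = 1.49 either way. No dropout rate is given. The profile is scaled to figures extrapolated from the highest-exposed individual with different multipliers for Cmax and AUC (1.71 and 1.54), so its shape need not be typical. The analysis is descriptive, and the precision statement and exposure margins rest on Cmax and AUC(0-24). All of this is fair and limits the weight of the point. But the shift is systematic and avoidable, and AUC(0-t) falls in every scenario tried.

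**Assay limit.** Completers who become non-quantifiable before 120 h also have a shorter t. That is how AUC(0-t) ordinarily behaves and is a different matter from sampling that stopped.

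**Conclusion.** The point holds for AUC(0-t), and it follows from the SAP's own definitions without any assumption about working practices. Any participant whose sampling stops before 120 h through withdrawal or a missed visit contributes a shorter-horizon area to the arm's summary, and replacement dilutes this only slightly.

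The sizes (3% to 14% for a 24 h end, 2% to 7% for a 48 h end, one person among six) rest on the assumed biexponential shape, the 46 h half-life and quantifiable concentrations to 120 h. The widening of the interval also rests on borrowing the AUC(0-24) SD.

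For t½ and AUC(0-∞) the finding is only that the SAP lacks a lambda_z acceptance rule; bias is possible but not established. Nor do the documents tie Phase 2b decisions to AUC(0-t) in particular: Protocol 3.1 speaks of the PK profile and systemic exposure in general.

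**What to change.** Before unblinding, amend SAP 10.5.1 and Table 4 as follows.

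1. Summarise AUC(0-t) in Tables 3.3 and 3.4 only for participants whose sampling reached 120 h, including those who became non-quantifiable earlier; or summarise it to a common t. List the remaining AUC(0-t) values in Listing 28 with a flag and the reason.
2. State a lambda_z acceptance rule: minimum number of points, fit and time span. Summarise t½ and AUC(0-∞) for early leavers only where it is met. A blanket exclusion would discard usable values, since a profile reaching 48 h often recovers both.
3. Leave the Table 4 rule for extrapolating AUC(0-24) when the last quantifiable time is before 24 h, subject to the same lambda_z rule.
4. Keep Cmax and tmax from these participants in the summaries, and AUC(0-24) where the 24 h sample exists.

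The cost is a few sentences. In an affected arm, n for AUC(0-t), and possibly for t½ and AUC(0-∞), may be one lower than for Cmax. If the lost participant is replaced, six full profiles remain.
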